5.2. Safety Assessment

The safety assessments/endpoints are

- adverse event (AE) reports, including the incidence of overall AEs, serious AEs (SAEs), and AEs (or SAEs) leading to discontinuations
- Clinical laboratory evaluations (serum chemistry, hematology, and urinalysis)
- Clinical evaluations (vital signs including orthostatic effects, and 12-lead ECGs)
- weight and body mass index (BMI)
- concomitant medication reports
- physical examinations
- Columbia – Suicide Severity Rating Scale (C-SSRS)

The following safety measurements will also be collected to assess the occurrence of symptoms of withdrawal from dasotraline:

- Cocaine Selective Severity Assessment (CSSA)
- Discontinuation-Emergent Signs and Symptoms (DESS) Scale
- Symptoms of anxiety utilizing the HAM-A
- Symptoms of depression utilizing the MADRS

5.2.1. Columbia – Suicide Severity Rating Scale (C-SSRS)

The C-SSRS is an instrument designed to systematically assess and track suicidal behavior and suicidal ideation for life time, one month prior to screening and throughout the trial. The strength of this suicide classification system is in its ability to comprehensively identify suicidal events while limiting the over-identification of suicidal behavior. The C-SSRS includes the following four sections: Suicidal Ideation, Ideation Intensity, Suicidal Behavior and Actual Suicide Attempts. The C-SSRS is administered by a trained rater at the site.

Severity of suicidal ideation is rated on a 6-point scale from 0='No ideation present' to 5='Active ideation with plan and intent'. A score of 4 or 5 on this scale indicates serious suicidal ideation. Subjects with Type 4 (active suicidal ideation with some intent to act, without specific plan) or Type 5 (active suicidal ideation with specific plan and intent) suicidal ideation during the study will be discontinued from the study and referred to a mental health professional. Suicidal ideation score is defined as the most severe suicidal ideation score (1-5 on the CSSRS) present at the assessment; assign a score of 0 if no ideation is present. The ideation intensity total score is calculated as summation of the five items from the Ideation Intensity scale: frequency, duration, controllability, deterrents, and reasons for ideation. If one or more of these 5 items are missing at a visit, no imputation will be made and the corresponding ideation intensity total score will be set as missing. Items corresponding to frequency and duration are each rated on a scale from 1 to 5 and items corresponding to controllability, deterrents, and reasons for ideation are each rated on a scale from 0 to 5. If the patient did not endorse any suicidal ideation, set the intensity rating to 0. Thus, the possible range for the intensity total score is 0 to 25.

Suicidal behavior is collected as presence/absence of actual attempts, non-suicidal self-injurious behavior, interrupted attempts, aborted attempts, preparatory acts or behavior, and any suicidal behavior. In addition, the number of actual attempts, interrupted attempts, and aborted attempts is captured. Any attempt will be defined as suicidal behavior.

The lethality associated with actual attempts is rated on a 6-point scale from 0='No physical damage or very minor physical damage' to 5='Death'. Potential lethality of attempts is rated on a 3-point scale from 0='Behavior not likely to result in injury' to 2='Behavior likely to result in death despite available medical care'.

The C-SSRS is collected at screening, Baseline, Weeks 1, 2, 3, 4, 6, 8, 10 and 12/EOT for randomized subjects, and at Weeks 13, 14 and 15 for subjects who enter the withdrawal period.

321

This study utilizes 2 versions of the C-SSRS. At the screening visit, the “Baseline/Screening” version will be completed. C-SSRS at ‘Baseline/Screening’ consists of two parts: part 1 – life time; part 2 – past 1 month. For all subsequent visits, the “Since Last Visit” version of the C-SSRS is administered.

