Efficacy will be evaluated at each visit using the subject binge eating diary and a clinician interview to assess the frequency of binge episodes and the number of binge days, defined as days with at least one binge episode. Additional assessments will include BE-CGI-S, Y-BOCS-BE, MADRS, HAM-A, SDS, and EDE-Q modified. Safety and tolerability will be monitored throughout the study by collection of physical examination results, ECGs, vital signs, AEs, clinical laboratory parameters, C-SSRS, body weight, and BMI will be calculated. Subjects who have significant findings for suicidal ideation upon completion of the C-SSRS at any time during the study must be referred to the Investigator for follow-up evaluation. Assessment of potential withdrawal effects will be conducted via administration of the CSSA, DESS, HAM-A, and MADRS at the end of treatment and during the 3-week study medication withdrawal period.

Blood samples for pharmacokinetics (PK) and biomarkers associated with eating disorders (to be determined) will be collected. Blood samples collected for PK assessment will be analyzed for plasma concentrations of dasotraline. The relationship between dasotraline plasma concentration and the primary and selected secondary clinical outcome measures will be evaluated. The relationship between biomarkers associated with eating disorders in relationship to the severity of BED and response to dasotraline will be evaluated at a later date in the development program. Plasma samples collected for PK and biomarker concentration analysis may also be used for the additional characterization of and/or bioanalytical method development for dasotraline.

A blood sample will be collected from subjects who provide separate informed consent for pharmacogenomics (PGx) analysis for potential evaluation of associations between genetic polymorphisms such as, but not limited to Taq1DRD2, OPRM1, and DRD4-7R, and the severity of BED, the clinical response to dasotraline, in addition to the safety, efficacy, and PK profiles of dasotraline to be conducted at a later date in the development program. Separate consent is required for collection of this specific blood sample and will be obtained at Screening for subjects who agree to provide this sample (note: this separate consent is not required for participation in the study, it is required only for subjects who will provide this sample).

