8. SELECTION OF SUBJECTS

Approximately 480 total subjects will be randomized (160 subjects per treatment group) at approximately 50 clinical sites in the United States.

The subject's eligibility assessment will be reviewed by the CRO's Clinical Surveillance Team (CST) along with the sponsor based on protocol specified inclusion and exclusion criteria to promote appropriate subject enrollment and data quality. For the prebaseline review, sites will be required to submit specific screening information for clinician and sponsor review, prior to proceeding to baseline. The sponsor will participate in the eligibility review process with the CRO to ascertain the subject's eligibility and will be copied on all communications between the CRO and the site. In the event the CRO/sponsor and site do not agree on a subject's eligibility, then the subject will not be enrolled. Decisions regarding inclusion of subjects and assessment of subject safety throughout the trial primarily remain at the discretion of the Investigator; however, the Medical Monitor or Sponsor may request exclusion or discontinuation of a subject based on entry criteria or subject safety.

Subjects must meet all inclusion criteria and no exclusion criteria at both the Screening and Baseline visits unless otherwise noted under the Inclusion or Exclusion Criteria. Eligibility criteria involving clinical laboratory values will be based on results from samples obtained at Screening.

Subjects may be rescreened once for out of range clinical laboratory results including UDS or ECG results following authorization of the medical monitor. Each time a subject is rescreened a new subject number will be assigned. Screening numbers cannot be reassigned to another subject.

Subjects whose study participation is prematurely terminated will not be replaced.

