11.4.2. Safety Scales

11.4.2.1. Columbia Suicide Severity Rating Scale (C-SSRS)

The C-SSRS ([Posner-2007](#)) is a tool designed to systematically assess and track suicidal AEs (suicidal behavior and suicidal ideation) throughout the study. The strength of this suicide classification system is in its ability to comprehensively identify suicidal events while limiting the over-identification of suicidal behavior. The scale takes approximately 5 minutes to administer. The C-SSRS will be administered by a trained rater at the site.

This study will utilize 2 versions of the C-SSRS. At the screening visit, the “Baseline/Screening” version will be completed; for all subsequent visits, the “Since Last Visit” version of the C-SSRS will be administered.

Subjects who answer “yes” to “suicidal ideation” item 4 (active suicidal ideation with some intent to act, without specific plan) or item 5 (active suicidal ideation with specific plan and intent) on the C-SSRS assessment at Screening (in the past month) must be referred to the Investigator for follow-up evaluation.

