13. TERMINATION OF SUBJECT FROM STUDY/DISCONTINUATION OF STUDY DRUG

13.1. Criteria for Study Drug Discontinuation

Subjects may be discontinued from the study drug at any time during the treatment period. The possible reasons for discontinuation of study drug are as follows:

- Adverse event
- Lack of efficacy (specify)
- Lost to follow-up (specify)
- Non-compliance with study drug (specify)
- Protocol violation (specify)
- Pregnancy
- Withdrawal by subject (specify)
- Other (specify)

If, at any time during the course of the treatment period, in the opinion of the Investigator, the subject may no longer safely participate due to a change in medical status (eg, experiences an AE, becomes pregnant), the subject must be discontinued from the study drug.

The primary reason and information for study drug discontinuation will be recorded on the appropriate CRF. In case of death, the date of death should be captured on the CRF.

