SIGMA	Structured Interview Guide for the MADRS
SOC	System organ class
TEAE	Treatment-emergent adverse event
tmax	Time to maximum concentration
UDS	Urine drug screen
ULN	Upper limit of normal
URS	User Requirements Specifications
USP	United States Pharmacopeia
VAS	Visual analog scale
WBC	White blood cells
Y-BOSC-BE	Yale-Brown Obsessive Compulsive Scale Modified for Binge Eating

321

1. Introduction

This statistical analysis plan (SAP) contains the definitions of analysis populations, derived variables, and statistical methods for the analyses of efficacy and safety data from study Dasotraline SEP360-321. It outlines the analyses to be performed for data collected both through the Week 12 visit and through withdrawal period. It is developed based on the version of the study protocol Version 3.00 dated Nov 17, 2017. This SAP is developed and finalized prior to database lock for unblinding of the clinical database for study SEP360-321.

If additional analyses are required to supplement the planned analyses described in the SAP after the database lock, they may be performed and will be identified in Clinical Study Report (CSR).

2. Study Objectives

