The study consists of 3 periods: Screening (up to 3 weeks), 12-weeks of treatment, and 3-week study drug withdrawal period. Subjects who complete the 12-week double-blind treatment period in this study may be eligible to enroll and continue treatment for an additional 12 months in an open-label extension study (Study SEP360-322). Subjects who do not enter the extension study complete the study drug withdrawal period in this study. See protocol Section 7.1 Figure 1 for study schematic.

Efficacy is evaluated at each visit using the subject binge eating diary and a clinician interview to assess the frequency of binge episodes and the number of binge days defined as days with at least one binge episode. Additional assessments include BE-CGI-S, Y-BOCS-BE, MADRS, HAM-A, SDS and EDE-Q modified. Safety and tolerability are monitored throughout the study by collection of physical examination results, ECGs, vital signs, AEs, clinical laboratory parameters, C-SSRS, body weight, and BMI. Subjects who have significant findings for suicidal ideation upon completion of the C-SSRS at any time during the study must be referred to the investigator for follow-up evaluation. Assessment of potential withdrawal effects is conducted via administration of the CSSA, DESS, HAM-A, and MADRS at the end of treatment and during the 3-week study medication withdrawal period.

Blood samples for pharmacokinetic (PK) and biomarkers associated with eating disorders to be determined are collected. Blood samples collected for PK assessment are analyzed for plasma concentrations of dasotraline. The relationship between dasotraline plasma concentration and the primary and selected secondary clinical outcome measures are evaluated. The relationship between biomarkers associated with eating disorders in relationship to the severity of BED and response to dasotraline will be explored at a later date in the development program. Plasma samples collected for PK and biomarker concentration analysis may also be used for the additional characterization of and/or bioanalytical method development for dasotraline.

A blood sample is collected from subjects who provide separate informed consent for pharmacogenomics (PGx) analysis for potential evaluation of associations between genetic polymorphisms such as, but not limited to Taq1DRD2, OPRM1, and DRD4-7R, and the severity

321

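### SAP 5.2.1 describes an automatic stop for on-study C-SSRS Type 4 or 5 ideation that the protocol does not contain

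*SAP*

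**What the plan says.** SAP 5.2.1, in its description of the scale, says that subjects with Type 4 or Type 5 "suicidal ideation during the study will be discontinued from the study and referred to a mental health professional". The sentence has no condition attached.

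The protocol says something different in each place where it deals with the matter:

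- Section 7.1 (and the synopsis): subjects with significant suicidal ideation findings "at any time during the study must be referred to the Investigator for follow-up evaluation". The section does not define significant.
- Section 11.4.2.1: items 4 and 5 are named, but a positive answer "on the C-SSRS assessment at Screening (in the past month) must be referred to the Investigator". This covers Screening only. Exclusion criterion 13 in Section 8.2 is likewise an entry rule applied at Screening.
- Section 13.1: if "in the opinion of the Investigator, the subject may no longer safely participate due to a change in medical status", then "the subject must be discontinued from the study drug". No C-SSRS threshold is listed.
- Section 8: "the Medical Monitor or Sponsor may request exclusion or discontinuation of a subject based on entry criteria or subject safety".

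SAP Section 3 (Study Design) repeats the protocol's general rule that significant findings "must be referred to the investigator for follow-up evaluation".

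**The concern.** The SAP describes a fixed stopping rule for the most serious levels of suicidal ideation. The protocol, which sites follow, has only referral followed by judgement. A subject who reports intent or a plan could therefore stay on blinded drug if the Investigator thought it safe, while a reader of the SAP would believe that every such subject had been stopped.

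The wording also differs on what is stopped. The SAP says the subject leaves the study. Protocol 13.1 stops study drug, and 13.3 then asks for the EOT and withdrawal visits. Those visits repeat the C-SSRS, so taking the SAP wording literally would end follow-up in the subjects who most need it.

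**Working it through.** The plan gives no figure to reproduce here. The check compares the texts and then bounds the size of the difference.

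1. The two rules side by side:

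| | SAP 5.2.1 | Protocol |
|---|---|---|
| Trigger | Type 4 or 5 at any time on study | On study: significant findings, undefined (7.1). Items 4 and 5 named for Screening only (8.2, 11.4.2.1) |
| Action | Discontinuation in every case | Referral; drug is stopped on Investigator judgement (13.1) or may be stopped at the request of the Medical Monitor or Sponsor (8) |
| What ends | Study participation | Study drug; EOT and withdrawal visits still requested (13.3) |
| Referral to | Mental health professional | Investigator |

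2. Could a fixed stop be implied in the protocol? Where it wants one, it writes one: after unblinding (7.2.3), after a confirmed pregnancy (12.4.2), and for suspected abuse or diversion (Appendix VII). Nothing comparable appears for the C-SSRS, so every on-study route to stopping for ideation is discretionary.

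3. Could a version difference explain it? This is unlikely. The SAP Introduction says "It is developed based on the version of the study protocol Version 3.00 dated Nov 17, 2017". Protocol 7.2.1 carries the single stratification factor that SAP 3.2 attributes to V3.00.

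4. How long could the rules diverge for one subject? Inputs are the visit days and windows in Protocol Table 2. A stop can change dosing after 7 visits (Weeks 1, 2, 3, 4, 6, 8, 10); at Week 12 treatment ends anyway. With one dose a day, the nominal gap to the next scheduled C-SSRS is 7 doses after Weeks 1 to 3 and 14 after Weeks 4 to 10. The longest gap is (next day + window) − (current day − window):
   - Week 1 to 2: (14 + 2) − (7 − 2) = 11; Weeks 2 to 3 and 3 to 4 have the same spacing and windows
   - Week 4 to 6: (42 + 3) − (28 − 2) = 19
   - Week 6 to 8: (56 + 3) − (42 − 3) = 20
   - Week 8 to 10: (70 + 3) − (56 − 3) = 20
   - Week 10 to 12: (84 + 1) − (70 − 3) = 18

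   The maximum before the next scheduled C-SSRS is therefore 11 doses early on and 20 later. Both are upper bounds, because the Investigator can act between visits.

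5. How many subjects? The planned regions in SAP Table 6.3 sum to 59 + 75 + 50 + 69 + 55 + 22 + 88 + 70 + 3 = 491. The actual regions give the same total: 127 + 37 + 138 + 3 + 62 + 17 + 24 + 80 + 3 = 491. The documents give no rate for items 4 and 5. Assuming 0.2% to 1%: 0.002 × 491 = 0.98 and 0.01 × 491 = 4.91, or about 1 to 5 subjects. The rules give different outcomes only for those whom the Investigator would have kept on drug, so 1 to 5 is a ceiling under that assumption.

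6. Does any analysis depend on the sentence? No. The C-SSRS endpoints in SAP 7.4.7 come from the recorded scores whatever was decided about dosing. For the efficacy analyses, at most about 5 of 491 extra discontinuations compares with a planned dropout allowance of (160 − 96)/160 = 40%.

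**The case against.** The strongest reply is that this is a stray sentence in a scale description. A SAP does not govern conduct, nothing in the analysis uses the sentence, and the protocol does not neglect on-study ideation. The C-SSRS is done at every visit, significant findings must be followed up, drug must be stopped if the Investigator judges that continuing is unsafe, the Medical Monitor or Sponsor can ask for a stop, and a DSMB reviews safety. Judgement after referral is a legitimate design. Nothing shows that the sponsor meant the stricter rule, so deleting the sentence would also remove the mismatch.

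Much of this stands. The protocol's approach is not unsafe in itself, and no result changes. What does not stand is leaving the sentence alone. The SAP tells readers what happened to these subjects, and the protocol does not ensure that it did. If subjects are still being dosed, the sponsor's own statement of a safety rule belongs where sites will see it.

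A reader might also infer that the SAP contradicts itself, because Section 3 gives only the referral rule. That reading is weak. Section 3 is the broader rule and 5.2.1 a narrower, stricter one, and a subject can fall under both.

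**Conclusion.** The concern holds as a mismatch between the documents on a safety rule. SAP 5.2.1 states an automatic on-study stop, and the protocol has none. It should be corrected because the topic is serious and the correction is cheap. The effect is small: at most about 1 to 5 of 491 subjects, assuming a 0.2% to 1% rate that the documents do not supply and assuming Investigators would stop none of them.

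Three stronger readings are tempting and not supported:

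- That dosing decisions for these cases could not be traced. SAP 6.2.1 lists all subject data by subject, 7.1.3 summarizes reasons for discontinuation, and 7.4.2 summarizes adverse events by action taken, lists discontinuations due to adverse events, and treats suicide and self-injury events as of special interest. Cases can be linked by subject.
- That the earlier BED study points to a risk of item 4 or 5 ideation on drug. Protocol 4.2 reports one SAE of suicidal ideation, with neither treatment arm nor grade.
- That a protocol amendment is certainly needed. SAP 6.1.7 already reports subject numbers at completion of enrollment, and the documents do not say whether anyone was still being dosed.

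**What to change.** If any subject is still being dosed:

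- State in Protocol 13.1 and 11.4.2.1 that any post-baseline C-SSRS ideation item 4 or 5 leads to discontinuation from study drug, with prompt Investigator evaluation, referral to a mental health professional, and the EOT and withdrawal visits under 13.3.
- Change SAP 5.2.1 to say discontinued from study drug, with a cross-reference to Protocol 13.1. SAP Section 3 needs no edit.

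The cost is two short protocol edits in one amendment with IRB approval (Protocol 17.5), a memo to sites and one SAP sentence. There are no new visits or assessments. Extra discontinuations would be at most the 1 to 5 above, on the same assumptions.

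If dosing has ended, correct SAP 5.2.1 to state the rule sites actually followed. Optionally, add one listing of post-baseline item 4 or 5 cases showing treatment, visit, action taken and disposition. It would mainly save the reader from matching existing listings. The cost is one sentence and, if wanted, one listing.

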5.2.2. Withdrawal Assessment for Physical Dependence and Withdrawal Symptoms

Subjects who either are early terminated in treatment period or complete 12-week treatment period but not enter into extension study need to complete the study medication withdrawal period assessments and visits.

Assessment of potential withdrawal effects will be conducted via administration of the CSSA, DESS, HAM-A, and MADRS at Week 12 (End of Treatment), then again at Weeks 13, 14, and 15 during the 3-week study medication withdrawal period. The CSSA and DESS will also be completed during the 3-week study medication withdrawal period on non-clinic visit days. Clinical site staff will call the subject every other day during the study medication withdrawal period, beginning the second day after the last dose of study drug, unless a clinic visit is scheduled for that day. Clinical site staff will record the responses in the subject’s source information and in the CRF with the contact date and time. A window of ± 1 day is allowed for each weekly clinic visit and telephone call. If the subject cannot be contacted on a given day, during the next contact the study site staff will retrospectively collect the missed CSSA and DESS, in addition to the current day’s CSSA and DESS.

5.2.2.1. Cocaine Selective Severity Assessment (CSSA)

The CSSA is a clinician-administered scale designed to evaluate withdrawal signs and symptoms related to stimulants over the past 24 hours. Included in the CSSA are those symptoms most often associated with early cocaine abstinence, including change in appetite, depression, fatigue, anhedonia, anxiety, irritability, sleep disturbance, and inability to concentrate, paranoia, carbohydrate craving, bradycardia, and suicidality. The CSSA scale contains 18 items. All items except item 14, are scored 0 to 7 according to instructions generally with 0 = no symptoms and 7 = maximum score on any individual item. Item 14 is scored 0 to 8 with 0 = no symptoms and 8 = maximum score. The score for each question will be summed to compute a total score ranging from 0 to 127 with higher score indicates severe withdrawal signs and symptoms. If the response to any question is missing, the total score will be missing.

The CSSA is collected at clinic visits: Week 12/EOT, and Weeks 13, 14 and 15 for subjects who enter the withdrawal period, as well as at phone contacts during the withdrawal period, beginning the second day after the last dose of study drug.

